6.3. Medical History

Medical history will be coded according to the Medical Dictionary for Regulatory Activities (MedDRA; Version 19.0 or higher). A frequency summary (number and percentage) of subjects with at least one medical history will be presented by system organ class (SOC), and preferred term (PT), with SOCs sorted in alphabetical order and PTs within each SOC in descending order of frequency for all subjects in the ITT and mITT sets.

In addition, A summary of the following will be presented by system organ class (SOC), and preferred term (PT) for subjects in the mITT set:

- History of recurrent VVC as evidence by applicable PT;
- Other vulvovaginal conditions (Selected SOC and Preferred Terms).

A by-subject listing of medical history will be provided.

6.4. Inclusion and Exclusion Criteria

Prior to enrollment, the investigator will assess if the subject fulfills all of the inclusion and none of the exclusion criteria outlined in the protocol (sections 11.1 and 11.2). The specific inclusion criterion not met or exclusion criterion which was met will be recorded in the eCRF. This information will be presented in a listing.

7. Treatments and Medications

7.1. Prior and Concomitant Medications

All prior and concomitant medications taken before Baseline (Day 1) through the TOC visit will be recorded. Only the use of antifungal medications, vaginal (topical) medications, antibiotics for any reason or any other medications to treat an AE will be recorded after the TOC visit through the last study visit (FU).

All prior and concomitant medications will be coded using the current version of the World Health Organization Drug Dictionary Enhanced (WHO-DD) and summarized by treatment group based on the ITT and mITT sets.

7.1.1. Prior Medications

Prior medications are defined as medications taken and stopped prior to the first dose of study drug. The number and percentage of subjects who took prior medications will be presented by WHO therapeutic drug class and generic drug name.

In addition, a summary of the following will be presented for subjects in the mITT set:

- Antibiotic use 30 days before baseline visit;
- Systemic steroid use 30 days before baseline visit.

7.1.2. Concomitant Medications

Concomitant medications are defined as medications started on or before the FU visit date with missing stop dates or stop dates after the first dose of study drug.

A summary showing the number and percentage of subjects who took concomitant medications will be presented by WHO therapeutic drug class and generic drug name.

A by-subject listing of prior and concomitant medications will be provided.

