13.0 Non-Study Treatments

13.1 Prior and Concomitant Medications

All medications (including prescription and over-the-counter medications, supplements, and herbal products) taken from 30 days before Baseline (Day 1) through the TOC visit (Day 8 - Day 14) will be recorded on the subject's diary and in the eCRF. Only the use of antifungal medications, vaginal (topical) medications, antibiotics for any reason or any other medications to treat an AE will be recorded after the TOC visit through the last study visit (FU). Start and stop dates of concomitant medications will be recorded in the eCRF. Prior and concomitant medications will be reviewed and recorded at all scheduled and unscheduled study visits.

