18.5 Prior and Concomitant Medications

Prior and concomitant medications will be coded using the World Health Organization Drug Dictionary terminology. The number and percentage of subjects taking each medication before and after the first dose of study drug will be tabulated by treatment group. Medications taken and stopped prior to the first dose of study drug will be considered prior medications. Medications started on or before the FU visit date with missing stop dates or stop dates after the first dose of study drug will be considered concomitant medications.

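### A medication whose stop date is the date of first dose meets neither the prior nor the concomitant definition, so it drops out of both descriptive tables

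*SAP*

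**What the plan says.** SAP 7.1.1: "Prior medications are defined as medications taken and stopped prior to the first dose of study drug".

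SAP 7.1.2 defines concomitant medications as those started no later than the date of the FU visit, "with missing stop dates or stop dates after the first dose of study drug".

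Protocol 18.5 has the same pair of rules: "Medications taken and stopped prior to the first dose of study drug will be considered prior medications", and those with missing stop dates or "stop dates after the first dose of study drug will be considered concomitant medications".

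On what is collected, Protocol 13.1 says: "Start and stop dates of concomitant medications will be recorded in the eCRF". Protocol 14.19 says the same. Neither section mentions a time of day for medications, and neither document gives a tie rule for a stop date that equals the first-dose date.

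SAP 7.1.1 also lists two further summaries for the mITT set: "Antibiotic use 30 days before baseline visit" and "Systemic steroid use 30 days before baseline visit".

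**The concern.** Two classes meant to cover all medication use should leave no gap. Here one side of the boundary is strictly before and the other strictly after, so equality belongs to neither. With day-level data, equality is an ordinary value: a course that ends on the day of first dose, or a single-day product taken on that day.

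The second case is the awkward one. A product taken on Day 1 after the first dose is plainly used alongside study drug, yet it is missing from the concomitant table. What is at stake is the completeness of two descriptive tables and of any statement in the study report that relies on them.

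**Working it through.** The plan states no figure on this point, so the check is whether the two rules cover every possible case.

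**Setup.** Put the first-dose date at day 0. Let *s* be the start day and *e* the stop day.

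- Prior (SAP 7.1.1, Protocol 18.5): *e* < 0.
- Concomitant (SAP 7.1.2, Protocol 18.5): *s* ≤ FU, and *e* missing or *e* > 0.
- FU is set at +24, the nominal Day 25 visit when first dose is on Day 1.

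**Patterns.** Starts run from −30 (Protocol 13.1 records medications from 30 days before baseline) to +24, which is 55 values. Stops run from *s* to +29, or are missing, giving 31 − *s* options for each start. The starts sum to 55 × (−3) = −165, so the total is 55 × 31 + 165 = 1705 + 165 = 1870.

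**Classification as written.**

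| Class | Count | Derivation |
|---|---|---|
| Prior | 465 | starts −30 to −1, stops up to −1: 1 + 2 + … + 30 |
| Concomitant | 1374 | starts −30 to 0: 31 × 30 = 930; starts 1 to 24: 24 × 31 − 300 = 444 |
| Neither | 31 | stop on day 0, starts −30 to 0 |
| Both | 0 | |
| Total | 1870 | 465 + 1374 + 31 |

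All 31 unclassified patterns have *e* = 0. One of them is *s* = *e* = 0, the product taken only on the day of first dose.

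**With *e* ≥ 0 in the concomitant rule.** The 31 patterns move to concomitant (1374 + 31 = 1405). Neither falls to 0, both stays at 0, and 465 + 1405 = 1870.

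The share 31/1870 (about 1.7%) counts date patterns with equal weight. It does not estimate how many women or records are affected.

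**The case against.** **The rules may be read on clock time.** Both definitions refer to the first dose as an event. SAP 7.2.1 uses the date and time of dosing, and the baseline definition in SAP section 4 allows for time where appropriate. On that reading, a product taken after dosing on Day 1 stopped after the first dose and is concomitant, while one finished beforehand is prior. Protocol 18.5 also tabulates use before and after first dose, which suggests that full coverage was intended. This is fair, and the eCRF itself is not in the documents. But a timed dose cannot be ordered against a medication known only by its date, and dates are all that the protocol says is recorded. The SAP did address this boundary for baseline: Protocol 18.3 takes assessments before the first dose, whereas SAP section 4 takes those before or on its date. The medication rules received no such wording.

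**The by-subject listing may show the record.** It may. But SAP 7.1.2 describes it as a listing of prior and concomitant medications, so a record in neither class has no stated place in it.

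**A reader might infer that the 30-day antibiotic and steroid summaries leave out courses still ongoing at first dose.** The text does not say so. They sit under the prior-medication heading, but they are introduced as an addition and carry no stop condition. A woman on an antibiotic at baseline, with a course begun earlier, fits the bullet as worded. The SAP is only silent on whether such courses count.

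**A reader might infer that Day 1 antifungal or topical use would escape the efficacy definitions.** It would not. Clinical failure in SAP 8.1 depends on use of such therapy up to the TOC visit, without reference to these classes, and rescue antifungals have their own summary and listing in SAP 7.1.3.

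**Conclusion.** The gap is real but minor. With dates compared at day level, every medication record whose stop date equals the first-dose date falls outside both definitions, in the SAP and in the protocol. This assumes that medication times are not collected or not used; if they were collected and programmed, the gap would close.

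The consequence is an undercount in the descriptive medication summaries. No endpoint, analysis set or inferential result depends on these classes. The documents give no frequency for such records, so a number of affected women cannot be stated. Nor do they give a basis for ranking Day 1 above other days for interactions or early adverse events; the dosing provisions even let the second dose fall on the following morning.

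**What to change.** In SAP 7.1.2 and Protocol 18.5, define concomitant as started on or before the FU visit date, with a missing stop date or a stop date on or after the date of first dose. In SAP 7.1.1 and Protocol 18.5, define prior as a stop date before the date of first dose.

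The cost is a few words and one comparison operator in the programs. The downside is that a drug finished on Day 1 just before dosing is counted as concomitant. That is the cautious direction, and it is consistent with how the rule already treats missing stop dates.

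An optional clarification in SAP 7.1.1 is one sentence saying that the 30-day antibiotic and systemic steroid summaries count any use overlapping the window, whether or not the course continued past first dose.

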7.1.3. Rescue Antifungal Medications

The number and percentage of subjects who took rescue antifungal medication, prior or on TOC, after TOC but before FU, at FU visit will be presented for the ITT and mITT sets.

A by-subject listing of rescue antifungal medications will be provided.

7.2. Study Treatments

Please refer to Section 3.3 for the details of the study treatment.

Data related to the study treatment will be presented in a listing.

7.2.1. Study Participation Calculation and Extent of Exposure

The duration of study treatment (hours) is calculated as (the date time of the second dose – the date time of the first dose + 1) / 3600 only for subjects who got both 2 study treatments. For subjects who only got 1 or none study treatment, the duration of study treatment will be missing.

The duration of study participation (days) is calculated as date of Study Completion/Termination recorded on the End of Study page – first dose date + 1. If the date of Study Completion/Termination on the End of Study page is missing, or if a subject is lost to follow-up, the latest available visit date will be used.

The cumulative doses taken across the treatment period is defined as the number of study drug dispensed minus the number of study drug returned. If the study drug bottle was not returned, the dose diary data will be considered for the cumulative dose calculation. When subject answered no dose missing, we can assume the cumulative dose is 4. When subject answered only 1 dose missing, we can assume the cumulative dose is 2. When subject answered 2 doses missing, we can assume the cumulative dose is 0 tablet. The cumulative dose is missing when subject didn't answer at least one missing dose question.

The duration of study participation, the number of drug administrations and the cumulative actual doses by treatment will be summarized by summary statistics.

All this exposure information will be presented in a listing.

7.2.2. Treatment Compliance

Treatment compliance is defined as the ratio of total study dose to the planned dose, in terms of percentage. Treatment compliance will be summarized descriptively.

Treatment compliance = the cumulative dose / the planned dose (4 tablets) *100%.

The treatment compliance will be classified as 0, 25%, 50%, 75%, and 100%. This categorical data will be summarized with the frequency and percentage of subjects by treatment group.

Non-compliance with dose regimen (example all four tablets taken as a single dose) will be captured based on investigator's review of subject diary.

8. Efficacy Analysis

The primary efficacy and secondary efficacy endpoints will be performed on the modified intent-to-treat set (mITT), the intent-to-treat set (ITT) and the per-protocol (PP) set. The mITT analyses will be considered primary; the ITT and PP analyses will be considered supportive of the primary analyses on the mITT population. The denominator for all percentages will be the number of subjects in that treatment within the analysis set of interest, unless otherwise specified.

8.1. Primary Endpoint

The primary efficacy endpoint is defined as the proportion of mITT subjects who have a clinical cure (complete resolution of signs and symptoms) at the test-of-cure (TOC) visit.

Clinical outcomes will be assessed at the TOC Visit (Day 11) according to the following definitions:

- Clinical cure: Complete resolution of signs and symptoms of vulvovaginal infection without need for further antifungal treatment and topical vaginal drug therapy for the treatment of vulvovaginal irritation/pruritus prior to or at the TOC visit. Specifically, for complete resolution, any sign or symptom should be absent (score = 0);
- Clinical failure: No response to therapy or incomplete resolution of signs and symptoms or use of additional vulvovaginal or systemic antifungal therapy or topical vaginal drug therapy for the treatment of vulvovaginal irritation/pruritus prior to or at the TOC visit. For the subject who early terminated before TOC visit and received additional vulvovaginal or systemic antifungal therapy or topical vaginal drug therapy for the treatment of vulvovaginal irritation/pruritus prior to or at the early termination visit, the subject is considered a clinical failure.

Signs of VVC will be defined as the presence of erythema, edema, or excoriation. Symptoms of VVC will be defined as itching, burning, or irritation.

Each vulvovaginal sign will be objectively scored based on severity as follows:

- 0 = none (complete absence of any signs or symptoms);
- 1 = mild (slight);
- 2 = moderate (definitely present);
- 3 = severe (marked, intense).

Each vulvovaginal symptom will be objectively scored based on severity as follows:

- 0 = none (I have no discomfort);
- 1 = mild (I have some discomfort, but it does not bother me much);
- 2 = moderate (I have discomfort, which is annoying, but not enough to affect what I am doing);
- 3 = severe (I have discomfort, which is annoying enough to affect what I am doing).

The composite score of the vulvovaginal signs and symptoms will be calculated according to the following rules and this scale has a total possible score of 18.

- If all items of the vulvovaginal signs and symptoms have been scored, the composite score is calculated as the sum of the individual scores of all 3 items of signs and 3 items of symptoms;
- If any sign or symptom is not done, the composite score will not be calculated and treated as a missing data except at FU visit;
- Subjects who are free of symptoms are not required per protocol to have a vaginal examination at FU visit, therefore signs are not considered missing. For subjects who do not present symptoms and have no sign rated at the FU visit, the composite score of the vulvovaginal signs and symptoms at the FU visit will be calculated as zero.

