18.6 Efficacy

18.6.1 Efficacy Assessments

The primary efficacy endpoint of the study is the percentage of subjects with clinical cure (complete resolution of signs and symptoms) at the TOC visit. Secondary efficacy endpoints include the percentage of subjects with mycological eradication (negative culture for growth of *Candida* species) at the TOC visit, the percentage of subjects with clinical cure and mycological eradication at the TOC visit, the percentage of subjects with complete resolution of symptoms at the FU visit, and the percentage of subjects with clinical improvement (partial or complete resolution of signs and symptoms with a total composite score no greater than 1) at the TOC visit and the absolute change in signs and symptoms score from Baseline to TOC and FU visits.

The following treatment outcome definitions will be used for the assessment of efficacy relative to baseline:

Clinical Outcome

- Clinical cure: Complete resolution of signs and symptoms of vulvovaginal infection without need for further antifungal treatment. Specifically, for complete resolution, any sign or symptom should be absent (score = 0) by the TOC visit.
- Clinical failure: No response to therapy or incomplete resolution of signs and symptoms or need for additional vulvovaginal or systemic antifungal therapy. If the

subject receives or self-administers topical drug therapy for the treatment of vulvovaginal irritation/pruritus such as topical analgesic or corticosteroid after completing treatment with the study drug and before the TOC visit, the subject is considered a clinical failure.

Mycological Outcome

- Mycological eradication: A subject with negative culture for *Candida* species.
- Mycological persistence: A subject with a positive culture for *Candida* species.

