8.2.3. Symptom Outcome

The percentage of subjects with complete resolution of symptoms at the Follow-up (FU) visit will be analyzed by Candida Species of the baseline yeast and overall, using the same inferential analysis employing the same methods as for the primary analysis as noted in Section 8.1.1. The subjects with missing Follow-Up data for the symptom outcome will be imputed as symptom persistence using the NRI method described in Section 4.4.

Symptom outcomes will be assessed at the FU Visit according to the following definitions:

- Symptom Resolution: All symptoms are absent (score = 0) without need for further antifungal treatment or topical vaginal drug therapy for the treatment of vulvovaginal irritation/pruritus prior to or at FU visit;
- Symptom Persistence: No response to therapy or incomplete resolution of symptoms or use of additional vulvovaginal or systemic antifungal therapy or topical vaginal drug

therapy for the treatment of vulvovaginal irritation/pruritus prior to or at FU visit. For the subject who early terminated before the FU visit and received additional vulvovaginal or systemic antifungal therapy or topical vaginal drug therapy for the treatment of vulvovaginal irritation/pruritus prior to or at the early termination visit, the subject is considered a symptom persistence.

In addition, a sensitivity analysis will be conducted based on the mITT set where the subjects with the imputed symptom outcome using the NRI method at the FU visit will be removed from the analysis.

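### SAP 8.1 changes the topical-drug part of the clinical failure definition in protocol 18.6.1, in both product scope and time window, and SAP section 11 does not declare it

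*SAP*

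**What the plan says.** **Protocol 18.6.1** (repeated in the synopsis) classes as a clinical failure a woman who "subject receives or self-administers topical drug therapy for the treatment of vulvovaginal irritation/pruritus such as topical analgesic or corticosteroid", where the use falls "after completing treatment with the study drug and before the TOC visit". The rule is set by what the product treats. It does not limit where the product is applied.

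**SAP 8.1** counts as failure "use of additional vulvovaginal or systemic antifungal therapy or topical vaginal drug therapy for the treatment of vulvovaginal irritation/pruritus". With its window, the topical-drug part reads "topical vaginal drug therapy for the treatment of vulvovaginal irritation/pruritus prior to or at the TOC visit". The cure definition there uses the same term: "without need for further antifungal treatment and topical vaginal drug therapy for the treatment of vulvovaginal irritation/pruritus". The SAP is therefore consistent within itself but differs from the protocol.

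**SAP section 11** lists two changes from the protocol: ANCOVA in place of ANOVA, and diabetes diagnosis added to the efficacy models. The topical-drug rule is not listed.

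**SAP 8.2.3** applies a similar rule to symptom resolution at follow-up (FU): "without need for further antifungal treatment or topical vaginal drug therapy for the treatment of vulvovaginal irritation/pruritus prior to or at FU visit". **SAP 8.2.4** does so for clinical improvement at TOC. The protocol sets no topical-drug rule for either endpoint.

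**Protocol 13.1** records all medications from 30 days before Baseline through TOC. After TOC the list is restricted: "Only the use of antifungal medications, vaginal (topical) medications, antibiotics for any reason", plus drugs given to treat an adverse event. Protocol 14.19 repeats this.

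**The concern.** The primary endpoint has two definitions, and a programmer working from the SAP would not know that it departs from the protocol. The two changes act in opposite directions on an individual's classification.

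- **Scope.** The word *vaginal* can leave out a product applied to the vulva. Protocol 14.11 rates signs on the vagina, the vulva or both, and the symptoms rated are burning, itching and irritation. A steroid or analgesic cream could lower those scores. Protocol 13.2 and Appendix A prohibit topical vaginal corticoids but do not name vulvar products or topical analgesics, so the failure rule is the main safeguard against masked outcomes.
- **Window.** With no start date, use before the first dose falls inside the SAP rule when it is read literally. Exclusion criterion 2 bars recent antifungals but not anti-itch products, so women with such use can be enrolled, and the use will be on record.

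The first change can produce false cures and the second false failures. At stake are the cure rate in each arm, the treatment difference, and agreement between the reported endpoint and the protocol's endpoint.

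**Working it through.** **1. The two rules side by side**

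| Element | Protocol 18.6.1 | SAP 8.1 |
|---|---|---|
| Product | Any topical drug for vulvovaginal irritation or pruritus | Topical vaginal drug for the same purpose |
| Examples | Analgesic, corticosteroid | None |
| Window start | After study drug is completed | Not stated |
| Window end | Before TOC | TOC included |
| Declared in SAP section 11 | n/a | No |

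**2. Test cases, read literally**

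| Case (all six items 0 at TOC, no antifungal) | Protocol | SAP |
|---|---|---|
| Vulvar steroid or analgesic cream on Day 6 | Failure | Cure |
| Intravaginal anti-itch product on Day 6 | Failure | Failure |
| Intravaginal anti-itch product before first dose only | Cure | Failure |

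The first and third rows conflict. For antifungals and symptomatic drugs together the SAP writes "use of additional vulvovaginal or systemic antifungal therapy or topical vaginal drug therapy". Using *vulvovaginal* for one and *vaginal* for the other in the same phrase makes the narrow reading plausible.

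**3. The plan's own figure.** Inputs from protocol 18.1 and SAP 4.1: cure 50% v 30%, 2:1 allocation, two-sided 5%, 90% power, Pearson chi-squared. With pooled variance, pooled rate (0.30 + 2 × 0.50)/3 = 0.4333 and k = 2:

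n(placebo) = [1.960 × √(1.5 × 0.4333 × 0.5667) + 1.2816 × √(0.30 × 0.70 + 0.50 × 0.50/2)]² / 0.20² = (1.1895 + 0.7418)² / 0.04 = 93.2, rounded up to 94.

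The total is 3 × 94 = 282, as stated, with power 90.2%. The point does not rest on this figure. It is only the baseline for step 5.

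**4. Weight of one woman.** If 80% are culture-positive, mITT is about 0.8 × 122 = 98 on placebo and 0.8 × 244 = 195 on ibrexafungerp. One reclassified woman moves the placebo rate by 1/98 = 1.0 point, or the ibrexafungerp rate by 1/195 = 0.5 point.

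**5. Illustrative range.** The documents give no usage rates, so every value of f is an assumption. Each calculation uses 188 v 94 women.

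- False cures: a share f of failures in each arm is masked and scored as cured, so p′ = p + (1 − p)f.
- False failures: a share f of cured women in each arm had pre-dose use only, so p′ = p(1 − f).

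| f | False cures: rates, difference, power | False failures: rates, difference, power |
|---|---|---|
| 0 | 50.0% v 30.0%, 20.0 points, 90.2% | same |
| 2% | 51.0% v 31.4%, 19.6 points, 88.7% | 49.0% v 29.4%, 19.6 points, 89.2% |
| 5% | 52.5% v 33.5%, 19.0 points, 86.3% | 47.5% v 28.5%, 19.0 points, 87.6% |
| 10% | 55.0% v 37.0%, 18.0 points, 81.9% | 45.0% v 27.0%, 18.0 points, 84.5% |

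With equal f in both arms, either error shrinks the difference. With unequal f the direction is open. For example, 2 points of false cures on placebo and 1 on ibrexafungerp give 51% v 32% (19 points, power 86.6%), whereas 2 points on ibrexafungerp alone give 52% v 30% (22 points, power 94.8%).

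**The case against.** Much of the case on the other side stands.

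- **The narrow reading is not certain.** The SAP does not define topical vaginal therapy and ties it to vulvovaginal irritation. Both documents use *vaginal* and *vulvovaginal* loosely; protocol 14.11 uses both words for the same examination. A programmer could include vulvar products. This stands: the false cure follows from one literal reading and is not a stated SAP rule.
- **The pre-dose reading is strained.** The rule sits in a post-treatment outcome definition, beside words that imply added therapy. This is fair, but the protocol states the start explicitly and the SAP dropped it.
- **Masked itching alone is not a cure.** Three investigator-rated signs must also be 0 at TOC. This stands and limits the number of false cures.
- **Secondary endpoints.** A reader might infer that SAP 8.2.3 and 8.2.4 also narrow a protocol rule. They do not. The protocol sets no such rule for those endpoints, so the SAP adds one.
- **Data after TOC.** A reader might infer that vulvar products will be absent from the FU data. That depends on how the site reads the recording list, which also covers drugs given for adverse events.

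A reader might also infer that the missing start date lets masked women count as cured. It cannot, because a wider window only adds failures. Only the word *vaginal* can create a false cure.

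None of this removes the mismatch between the two primary definitions or its absence from section 11.

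**Conclusion.** The point holds as an undeclared conflict between protocol and SAP in the primary endpoint. Taken literally, the two rules classify some women differently: a vulvar-cream user with all scores at 0, and a cured woman with pre-dose use only. The changes to scope and window act in opposite directions on the cure rate and should be judged separately.

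The size is unknown because the documents give no usage rates. It is probably small: at an assumed 2% in both arms, either error takes about 0.4 point off a 20-point difference and 1.0 to 1.5 points off power. A firm claim of bias in one direction is not supported. Equal shares shrink the difference, but unequal use could shrink or enlarge it. The planned sample size of 282 evaluable women is unaffected. The matter deserves correction because it concerns the primary definition and is cheap to settle while the data are blinded.

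**What to change.** Before unblinding:

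1. **SAP 8.1.** In the cure and failure definitions, use the protocol's product scope: topical drug therapy for vulvovaginal irritation or pruritus, including analgesics and corticosteroids, not limited to vaginal products. Start the window after study drug is completed. State one end point, before TOC or including TOC, and use it in both documents. The alternative is to keep the SAP wording and declare and justify the change in section 11.
2. **SAP 8.2.3 and 8.2.4.** Use the same scope and start point for consistency, and state in section 11 that these topical-drug rules are added by the SAP.
3. **FU recording.** If the FU rule is meant to cover vulvar products, reconcile it with the post-TOC recording list in protocol 13.1 and 14.19, which names only vaginal (topical) products.

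**Cost.** The primary endpoint needs wording only, because all medications through TOC are already recorded and either rule can be programmed. Covering vulvar products at FU would also need a phrase in the protocol and the eCRF guidance. The sample size is unchanged; the cure rate may shift slightly in each arm.
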